#### Preliminary results:

Table 1. Physiological findings\*

	OAS (n=6)	RA (n=4)	P
Post-atherectomy			
Coronary Flow (1/s)	1.78±.21	1.41±.62	0.25
Index of microcirculatory resistance (a.u)	21±6	31±7	0.04
Coronary wedge pressure (mmHg)	21±6	27±6	0.15

± standard deviation; \*preliminary nonrandomized data.

#### Risks:

The risks associated with this study will involve the risks of inserting wires into the coronary arteries and with the administration of adenosine. The study protocol calls for an additional intracoronary wire insertion for physiology measurements. The risks include extra fluoroscopy time (approximately 10-20 seconds), extra contrast (less than 10 mL), and a <1% risk of coronary artery damage (dissection or perforation). Adenosine is used to measure FFR. The most common adverse effects of adenosine are headache, facial flushing, bronchospasm, and conduction abnormalities. Performance of FFR is generally safe, but does require placement of a wire and catheter in the coronary artery which can rarely cause injury to the artery.

There are no risks for an MRI and few, if any, side effects. The test does not use radiation, and to date, there have been no documented side effects from the radio and magnetic waves it uses. Allergic reactions to the dye are rare. Individuals with claustrophobia may feel uncomfortable in the MRI machine.

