**General Exclusion Criteria:**

- 1) Estimated creatinine clearance  $<30$  ml/min using Cockcroft-Gault equation, unless the patient is on dialysis;
- 2) STEMI within 24 hours of initial time of presentation to the first treating hospital, whether at a transfer facility or the study hospital.
- 3) PCI within 24 hours preceding the study procedure.
- 4) Cardiogenic shock (defined as persistent hypotension (systolic blood pressure  $<90$  mm/Hg for more than 30 minutes) or requiring pressors or hemodynamic support, including IABP, at time of procedure.
- 5) Mobitz II second degree or complete heart block
- 6) Malignant ventricular arrhythmias requiring treatment
- 7) Pulmonary edema defined as patient with shortness of breath, evidence of volume overload on physical exam, and crepitations on physical exam ( $>1/3$  of lungs) or radiographic interstitial or alveolar pulmonary edema
- 8) Subject is intubated.
- 9) Known LVEF  $<35\%$ .
- 10) Severe valvular disease (e.g. severe mitral regurgitation or severe aortic stenosis)
- 11) Patient is participating in any other investigational drug or device clinical trial that has not reached its primary endpoint.
- 12) Women who are pregnant or breastfeeding (women of child-bearing potential must have a negative pregnancy test within one week before treatment).

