### Procedures:

**Physiological indices:** Subjects will be randomized on a 1:1 basis to OAS versus RA. In both groups, we will perform sequential physiological interrogation of the coronary vasculature before and immediately after atherectomy and at the end of PCI, utilizing a direct and robust assessment of microvascular function. This will be achieved by measurement of the mean transit time ( $T_{mn}$ ) of saline using a single pressure-temperature sensor-tipped coronary wire (Certus™ guidewire, St Jude Medical, St Paul, Minnesota). The following parameters will be assessed:

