#### (2) Microvascular resistance ( $P_d * T_{mn}$ )

Extrapolating from Ohm's law, distal coronary pressure ( $P_d$ ) divided by the inverse of the hyperemic mean transit time (a correlate to absolute flow), measured simultaneously with the coronary pressure wire, will evaluate microvascular resistance. Under peak hyperemia (achieved by intravenous infusion of adenosine at 140  $\mu$ g/kg/min) this ratio has been called the IMR^3. IMR is derived from the assumption that at peak hyperemia the variability of resting vascular tone and hemodynamics will be eliminated, and the *minimum* microvascular resistance will be achieved.

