#### (4) CFR ( $T_{mn}$ at rest/ $T_{mn}$ at hyperemia)

The indication for PCI will be based on measurement of FFR, the current standard of practice, which will be determined as:

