#### (5) FFR ( $P_d/P_a$ at hyperemia)

where  $P_a$  is the aortic pressure measured by the guiding catheter at peak hyperemia. PCI is indicated in stenoses with FFR <0.8.

$T_{mn}$  under basal condition followed sequentially by IMR, FFR and CFR under maximum hyperemia will be measured at 3 separate time points: 1) pre-atherectomy, 2) immediately post atherectomy and 3) at the end of the PCI.

	Screening	Procedure	Post Procedure	Discharge
Consent	X			
Medical History	X			
Randomization	X			
CK/MB			X 	
Troponin I			X 	
Physiological Measurements (FFR)		X 		

X 4-8 hours post procedure; if positive again at 12-18 hours

X Physiological measurements (Total coronary flow, Microvascular resistance, Coronary wedge pressure, Coronary flow reserve and Fractional flow reserve) will be taken before and immediately after atherectomy and at the end of PCI)

**Sample Size:** A clinically important difference would be 20% reduction in IMR in OAS, equating to an IMR difference of 7 (SD=8,  $\alpha$  =0.05 and power=0.80) and requiring a total sample size of 20.

**Projected time for completion:** 1 year. CUMC has a large volume for PCI with ~ 3000 number of PCIs per year including ~250 procedures requiring atherectomy.

**Significance of the results:** If OAS is shown to cause lower disruption and loss of coronary microcirculatory function, the use of this atherectomy device may have significant favorable impact on myocardial recovery and function post PCI as compared to RA, potentially leading to prevention of major adverse cardiovascular events.

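### Adenosine hyperemia is scheduled three times in both arms and bronchospasm is named as a common effect, but no eligibility criterion covers bronchospastic disease or known adenosine intolerance

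*Combined protocol and SAP*

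**What the plan says.** The Procedures section has both randomized groups undergo physiological measurement "before and immediately after atherectomy and at the end of PCI". The section on microvascular resistance states how peak hyperemia is reached: it is "achieved by intravenous infusion of adenosine at 140" µg/kg/min. The FFR section repeats the schedule: "IMR, FFR and CFR under maximum hyperemia will be measured at 3 separate time points".

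The Risks section treats the drug as a hazard of the research: "The risks associated with this study will involve the risks of inserting wires into the coronary arteries and with the administration of adenosine". It then says: "The most common adverse effects of adenosine are headache, facial flushing, bronchospasm, and conduction abnormalities".

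The General Exclusion Criteria have 12 items. Two are respiratory: item 7, which begins "Pulmonary edema defined as patient with shortness of breath, evidence of volume overload on physical exam", and item 8, which excludes intubated patients. The schedule table puts medical history and randomization both at Screening. The Safety Monitoring Plan makes the principal investigator responsible for patient safety and has adverse events reviewed. It contains nothing specific to adenosine.

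**The concern.** The protocol requires a drug for its measurements and names bronchospasm among that drug's commonest effects, but it does not turn the warning into an eligibility rule. A patient with active asthma or a previous bad reaction to adenosine can meet every criterion and be randomized. Two outcomes then follow:

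- The patient is given adenosine for readings that serve the study.
- The operator withholds it, and a randomized patient has no hyperemic measurement. IMR is defined at peak hyperemia and is the quantity on which the sample size is based.

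The first is a matter of patient safety and is the main ground for the point. The second is a smaller matter of data completeness in a trial of 20.

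**Working it through.** The check is mostly a comparison of sections. The only arithmetic is counting.

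**1. Exposure.** Two arms, 3 hyperemic time points each, with intravenous adenosine as the stated method. That gives 3 scheduled hyperemia periods per patient. The wedge-pressure section also places adenosine between two post-atherectomy readings. It does not say whether this is a separate dose, so it is not counted.

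**2. How much of this serves the study.** The first period may be clinical, since the CFR section says: "The indication for PCI will be based on measurement of FFR, the current standard of practice". The other 3 − 1 = 2 periods come after atherectomy, when the decision to treat has been made. The only clinical use the protocol states for FFR is to establish the indication, so these two are scheduled for study readings.

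**3. Eligibility items searched.**

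| List | Items | On bronchospastic disease | On adenosine intolerance |
|---|---|---|---|
| Inclusion Criteria | 5 | 0 | 0 |
| Angiographic inclusion criteria | 2 | 0 | 0 |
| General Exclusion Criteria | 12 | 0 | 0 |
| Angiographic Exclusion Criteria | 6 | 0 | 0 |
| Total | 25 | 0 | 0 |

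The two respiratory exclusions do not fill the gap. Item 7 is defined by fluid overload with crepitations or by radiographic edema. Item 8 concerns airway status at the time. Neither reaches a patient with asthma.

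**4. Other written safeguards.** None of the 25 items lets the investigator exclude a patient on clinical judgment. Medical history is collected at Screening, but no criterion is tied to a bronchospastic history or an earlier adenosine reaction. The Safety Monitoring Plan has no adenosine-specific screening or stopping rule.

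**5. Consequence of withholding after randomization.** Randomization is at Screening, before the procedure. If adenosine is then withheld, that patient has no IMR. One such patient is 1/20 = 5% of the trial. With 1:1 allocation and about 20/2 = 10 per arm, that is about 1/10 = 10% of one arm.

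No figure in the protocol's sample-size statement depends on this point.

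**The case against.** **The harm step is not in the documents.** The Risks section lists bronchospasm as a general effect. It does not say that asthma or earlier intolerance raises the risk, and it does not mention intolerance at all. This stands. The link is a clinical assumption, though a modest step from the protocol's own warning.

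**A missing exclusion is not an order to dose.** History is taken, the principal investigator answers for safety, and the operator giving adenosine can decline to. Restating a drug's ordinary cautions in a short single-center protocol is partly a matter of preference. This lowers the weight of the point but does not remove it, because those safeguards depend on individual judgment and, used after randomization, cost the reading. The consent form is not in the available text and may carry a warning, but a consent warning would not be an eligibility rule.

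**Stronger readings a reader might infer.**

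- *That the conduction hazard is also inadequately covered.* Item 5 excludes "Mobitz II second degree or complete heart block". The Risks section speaks of conduction abnormalities generally, but nothing in the documents identifies a further disorder that should be excluded. That is a clinical judgment they do not settle.
- *That all the adenosine is for research, because the Alternatives section says patients who decline will not undergo FFR.* The same sentence says they are treated with or without FFR. It contradicts itself and cannot carry that conclusion. The first reading may well be clinical.
- *That some number of the 20 patients can be expected to be harmed.* The documents give neither the prevalence of such histories nor an event rate. An assumed prevalence would in any case describe how many patients have the history, not how many come to harm.

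**Conclusion.** The point holds as a limited gap in eligibility. Of 25 criteria, none addresses bronchospastic disease or known adenosine intolerance, although each patient is scheduled for 3 adenosine hyperemia periods, 2 of them for study readings, and the protocol itself names bronchospasm.

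The conclusion rests on one clinical assumption: that existing bronchospastic disease or earlier intolerance makes adenosine more hazardous. The number of patients affected cannot be derived from the documents and may be zero. The effect on the trial's inference is minor, confined to a possible missing IMR in a patient randomized before the problem is recognized. This is an inexpensive improvement that the sponsor could make. It is not a flaw that undermines the comparison of the two devices.

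**What to change.** Add one item to the General Exclusion Criteria, checked from the Screening medical history before randomization:

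*Active or severe asthma or other bronchospastic lung disease, or known hypersensitivity or intolerance to adenosine, or investigator judgment that adenosine is unsafe.*

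The wording is deliberately limited to active or severe disease. Excluding every patient with mild or inactive asthma would narrow eligibility more than the concern requires, and the discretion clause covers doubtful cases.

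The cost is one line in an amendment, slightly narrower eligibility and possibly a few extra screen failures. The site reports about 250 atherectomy procedures a year against a target of 20 patients, so recruitment should absorb this. No new assessment is needed, because the history is already collected at Screening. Since randomization is listed at the same visit, the amendment should say that the history is checked first.

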#### **Radiation Risk**

A small amount of radiation is needed for this research (about  $\frac{1}{2}$  millisievert). The extra lifetime risk of dying from cancer due to this radiation may be one in 50,000. The chances of a person dying of cancer with no extra radiation exposure are about one in 4. At such low radiation exposures, scientists disagree about the amount of risk. These estimates are very uncertain. An amount of radiation greater than usual is needed for this research.

#### **Benefits:**

Conducting FFR may provide the operator with additional information about the anatomy and physiology of the patients heart and further assistant in the direction of their course of treatment. Future patients will benefit from the knowledge gained from conducting this study.

#### **Alternatives**

Patients who do not consent to participate in the research will be treated with whichever device the operator prefers (OAS versus RA) with or without FFR and will not undergo FFR. All other procedures are standard of care.

#### **Safety Monitoring Plan**

The PI ([name] will be responsible for monitoring and patient safety for the full duration of the study. Adverse events will be reviewed and all unanticipated problems will be reported to the IRB in accordance with Columbia University Medical Center IRB Policies and Procedures.

